### D.5. Follow-up Clinic Visits and Phone Calls

Follow-up clinic visits will be conducted when subjects are in stable clinical status, where at least 2 weeks have elapsed since the time of their last prednisone or antibiotic course for treatment of a COPD exacerbation. Participants in both arms will be seen in our research clinics at months 3, 6, and 12 (Table 5). At each follow-up visit, study staff will remind participants not to disclose treatment arm. Subjects will be reminded that they should be working to slowly and steadily increase their walking and exercise. Subjects will perform 6MWT, spirometry, and HRQL assessments. All changes in medication or clinical status will be noted, any potential adverse events recorded, and a history of any COPD exacerbations or hospitalizations in the previous 3 months ascertained. We will also assess dyspnea (UCSD Shortness of Breath Questionnaire and MMRC Scale), physical activity (CHAMPS and [name]), and depression (Beck Depression Inventory). Subjects will also complete the following questionnaires: the Barriers to Exercise, Physical Activity Recall, VR-36, MOS Social Support, Bristol's COPD Knowledge, Exercise Self-Efficacy, Epworth Sleepiness Scale, the Brief Pain Inventory (short form, administered at C03, C06 and C12), and the Dietary Questionnaire (only administered at C00 and C12). The intervention subjects will also complete the Intervention Feedback Questionnaire that asks about the subject's experience with the study website and pedometer at the 6-month and 12-month in-clinic study visits. Blood for inflammatory biomarkers will be drawn by venipuncture, packed in a shipping container with an ice pack, and transported to the MAVERIC blood lab for processing and storage. Subjects recruited at VA Boston will be asked to complete DXA scans for body composition and bone mineral density at the 12-month in-clinic visit, and additionally will be asked to complete a body composition measurement using the Omron HBF-306CN. We will exclude any subject with a pacemaker or defibrillator to minimize any potential risks. If subject has previously undergone a DXA scan at the VA Boston Osteoporosis Clinic within 6 months, then the data from the Osteoporosis Clinic may be used and subject does not need to complete a scan specifically for the research study. If a subject does not complete the study-related questionnaires during the in-clinic visit, research staff will contact the subject after study visit by phone to finish the questionnaires over the phone or send the questionnaires home with the subject to be completed and returned in a pre-paid mailer.

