### **Statistics (power analysis)**

Prior to analyzing the outcomes, we will summarize and compare baseline demographic and clinical variables by treatment group. Any unbalanced characteristics occurring despite randomization will be assessed as potential confounders in multivariate analyses. Analyses will be performed with the SAS statistical software package (9.3, SAS Institute; Cary, NC).

**Primary Aim:** To determine the efficacy of the WEB intervention to increase 6MWT distance.

We focus on 6MWT distance at 6 months since we predict that the greatest difference in 6MWT distance between study arms will occur at month 6, at the end of the interventional phase. We have revised our statistical analysis plan to use 2-way factor analysis or analysis of variance (ANOVA). This approach will assess the effect of intervention versus control on 6MWT distance, using absolute measures of 6MWT distance at baseline and 6 months. Two-way ANOVA will allow us to assess the effect of treatment (intervention versus control), and additionally allow us to assess the interaction between treatment and time (treatment-time) on 6MWT distance. We will use a mixed model (PROC MIXED in SAS) to perform the 2-way ANOVA given its flexibility of modeling the variances and covariances, its robustness in accounting for correlated data (repeated measures data), and its flexibility in handling missing data. Models will have 6MWT distance as the dependent variable, and treatment, time, and treatment-time as independent variables. In this approach, models will also include study site and any unbalanced baseline characteristics as covariates. Primary analyses to determine the effect of WEB on 6MWT distance will use the intention-to-treat approach to include as many randomized subjects as possible in the analyses. Subjects will be considered to be in his/her randomly assigned arm no matter how much he/she participated in it. As a sensitivity analysis, however, we will examine 6MWT distance on a per-protocol basis, where noncompliant subjects ( $\geq 30\%$  of days with no exercise performed on logs) in each treatment arm will be excluded from the analysis.

**Anticipated Results:** We anticipate that subjects in the intervention group will have significantly higher 6MWT distance than subjects in the control group at 6 months.

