**Power Calculation:** This study is powered on our pre-specified primary outcome of 6MWT distance. Our main comparison is 6MWT distance at 6 months between the WEB intervention and control arms. Our power analysis is based on a widely accepted minimum clinically meaningful change in 6MWT distance of 54 meters and the published standard deviation for 6MWT distance of 80-120 meters (90). Our data in a similar Veteran population showed a standard deviation of 102 meters for 6MWT distance. We use a standard deviation of 100 meters in our power calculation. Using the sample size formula for the comparison of the means of 2 independent samples, we calculate that 55 evaluable subjects in each arm at 6 months will allow

[figure not shown]

detection of a difference of at least 54 meters between the WEB and usual care arms with a power of 80% and  $\alpha=0.05$ . We anticipate a maximal drop-out of 40% at 6 months. In order to have 111 evaluable subjects at 6 months, we plan to enroll a total of 185 subjects.

**Secondary Aims:** To estimate the effect of the WEB intervention on (a) HRQL, as measured by the St. George's Respiratory Questionnaire (SGRQ), (b) dyspnea, (c) CRP and IL-6, (d) risk of AEs and COPD-related hospitalizations, (e) engagement in PA as measured by daily step count, (f) body composition and bone mineral density, and (g) pain.

Our statistical analysis plan for the secondary outcomes is similar to that for the primary outcome. We will use 2-way factor analysis or analysis of variance (ANOVA) to assess the effect of intervention versus control on SGRQ-TS, dyspnea score, CRP and IL-6, and daily step count. We will analyze absolute values of the secondary outcomes at baseline and 6 months. Two-way ANOVA will allow us to examine the effect of our intervention, and additionally allow us to assess the interaction between treatment and time (treatment-time) on the secondary outcomes. We will use a mixed model (PROC MIXED in SAS) to perform the 2-way ANOVA. Models will have SGRQ-TS, dyspnea score, CRP and IL-6, or daily step count as the dependent variable, and treatment, time, and treatment-time as independent variables. Models will also include study site and any unbalanced baseline characteristics as covariates.

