### **Additional Analyses**

Additional analyses will be conducted with repeated measures ANOVA using all time points--baseline, 3, 6, and 12 months assessments of 6MWT distance--to explore the effect of the interaction between treatment and time (treatment\*time), as well as the between-subject group treatment effect (intervention versus control) and the within-subject effect (repeated over time) on 6MWT distance. We will use a mixed model (PROC MIXED in SAS) to perform the repeated measures ANOVA. We will examine both compound symmetry and AR(1) correlation structures. Models will have 6MWT distance at each time point as the dependent variable, and treatment,

time, and treatment-time as independent variables. Models will also have study site and any unbalanced baseline subject characteristics as covariates. Similarly, additional analyses will be conducted with repeated measures ANOVA using all time points--baseline, 3, 6, 9, and 12 months assessments of the secondary outcomes--to explore the effect of the interaction between treatment and time (treatment-time), as well as the between-subject group treatment effect (intervention versus control) and the within-subject effect (repeated over time) on SGRQ-TS, dyspnea score, CRP and IL-6 levels, and daily step count. We will use a mixed model (PROC MIXED in SAS) to perform the repeated measures ANOVA. Models will have the secondary outcome at each time point as the dependent variable, and treatment, time, and treatment-time as independent variables. Models will also have study site and any unbalanced baseline subject characteristics as covariates.

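### The primary mixed model uses only baseline and month-6 walks; the month-3 walk enters by single imputation or an exploratory model, and the plan does not say whether observed or imputed data are analyzed

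*Combined protocol and SAP*

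**What the plan says.** Under Statistics (power analysis), the primary analysis works "using absolute measures of 6MWT distance at baseline and 6 months". "Models will have 6MWT distance as the dependent variable, and treatment, time, and treatment-time as independent variables", with study site and unbalanced baseline characteristics as covariates. One reason given for choosing PROC MIXED is "its flexibility in handling missing data". The secondary outcomes follow the same pattern: "We will analyze absolute values of the secondary outcomes at baseline and 6 months".

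Month-3 walks exist. Section D.5 says "Participants in both arms will be seen in our research clinics at months 3, 6, and 12" and "Subjects will perform 6MWT, spirometry, and HRQL assessments"; Table 5 marks the 6MWT at month 3.

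The month-3 walk has two routes into the analysis:

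- **Imputation.** Minimizing Attrition and Handling Missing Data fills missing outcomes with the least favorable earlier value after worsening COPD or death, and otherwise with the last observed value. Table 2 repeats this. A complete-case analysis is the sensitivity check.
- **Exploratory model.** "Additional analyses will be conducted with repeated measures ANOVA using all time points--baseline, 3, 6, and 12 months assessments of 6MWT distance", under a heading separate from the primary aim.

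The statistics section does not mention imputation, and the missing-data section does not mention the mixed model's own handling of missing values. On attrition the plan says: "We anticipate a maximal drop-out of 40% at 6 months".

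**The concern.** A likelihood-based mixed model earns its advantage with missing data by conditioning on what was seen before drop-out. With two time points, a subject who walks at month 3 and then leaves supplies only a baseline value, which carries no information about response to treatment. The missing-at-random assumption then rests on baseline distance and covariates alone.

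Different selection in the two arms is plausible. Participants know their assignment. WEB participants receive weekly goals, Monday calls and upload reminders; control participants have no scheduled staff contact between the randomization call and month 3. The plan will compare losses by arm, but its remedy is to add baseline covariates, and these cannot correct drop-out that depends on month-3 response.

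If the imputation rule applies instead, the error is of another kind: a month-3 or baseline walk stands in for the month-6 walk, although the plan predicts the largest difference at month 6. The primary estimate therefore depends on a choice the plan does not make.

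**Working it through.** **1. The plan's own figures.** Inputs: 54 m, SD 100 m, 80% power, α = 0.05 (taken as two-sided).

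n per arm = 2 × (1.960 + 0.842)² × 100² / 54² ≈ 53.8, so 54. The t-based value is 54.8, so 55, with power 80.1%. Total: 111 / (1 − 0.40) = 185. These reproduce. Up to 0.40 × 185 = 74 subjects may lack a month-6 walk.

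**2. What a subject who leaves after month 3 contributes.**

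| Reading | Contribution |
|---|---|
| Two-point model, observed data | Baseline only |
| Two-point model after imputation | Baseline, plus a month-3 or baseline walk entered as month 6 |
| Three-point model, observed data | Baseline and month 3, each at its own time |

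**3. Assumptions not in the documents.** Correlations (baseline-month 3 / baseline-month 6 / month 3-month 6) of 0.85/0.80/0.85 or 0.75/0.65/0.75; 15% lost before month 3 and 25% after (total 40%). Selective drop-out means that the log-odds of leaving after month 3 rise by 1 per SD of worse month-3 change. The true month-6 effect is 54 m.

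**4. Observed data.** The estimate is the arm difference in change from baseline to month 6.

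- Two-point: regress month 6 on arm and baseline in completers. Effect = b_arm + (b_base − 1) × baseline difference.
- Three-point: regress month 3 on arm and baseline in month-3 attenders and month 6 on arm, baseline and month 3 in completers, then combine. With monotone drop-out both equal maximum likelihood.

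| Drop-out pattern | Correlations | Two-point | Three-point | Two-point bias |
|---|---|---|---|---|
| Selective, WEB only | 0.85/0.80/0.85 | 62.5 m | 53.9 m | 62.5 − 54 = +8.5 m |
| Same, half strength | 0.85/0.80/0.85 | 58.6 m | 54.2 m | +4.6 m |
| Selective, control only | 0.85/0.80/0.85 | 45.4 m | 53.8 m | −8.6 m |
| Selective, WEB only | 0.75/0.65/0.75 | 63.8 m | 53.6 m | +9.8 m |
| Equally selective in both arms | 0.85/0.80/0.85 | about 54 m | about 54 m | about 0 |

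In the first row the complete-case estimate is 64.0 m, so that sensitivity analysis moves with the biased estimate. With no true effect and the same WEB-only selection, the two-point test rejects about 11% of the time instead of 5% (about 7% at half strength).

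A second set of assumptions (stronger dependence, baseline-month 6 correlation 0.7-0.8, month 3-month 6 correlation 0.8-0.9, 25-75% of drop-outs having a month-3 walk) gave 61-70 m for the two-point model and about 54 m for the three-point model under WEB-only selection. The size follows the assumptions; the ranking of the two models does not.

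**5. Precision under random drop-out.** Take 55.5 completers and 92.5 randomized per arm, with baseline-month 6 correlation 0.80. Two-point variance = 2 × 10,000 × (1 − 0.80²) / 55.5 + (1 − 0.80)² × 2 × 10,000 / 92.5 = 129.7 + 8.6 ≈ 138.4, so SE 11.8 m. Simulation gives 11.8 m against 11.4 m with month 3 added, a saving of 0.4 / 11.8 = 3%. For 0.75/0.65/0.75 it is 15.2 against 14.6 m, or 4%.

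**6. If the imputation rule governs.** Assume a 27 m effect at month 3. Under random drop-out the expected last-value estimate is 0.60 × 54 + 0.25 × 27 + 0.15 × 0 = 32.4 + 6.75 + 0 ≈ 39 m. Across the selection patterns and both rules, simulation gives about 34-43 m. Even if the full 54 m were reached by month 3, the random-drop-out figure would be 32.4 + 13.5 = 45.9 m, because subjects lost before month 3 carry a baseline walk and count as no change.

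**The case against.** The strongest reply is that the plan does use month 3. Last-value and least-favorable imputation draw on that walk, and the additional analysis fits all visits. That is correct: a reader might infer that the month-3 walk is discarded, and the documents do not support this. But neither route does the job. Imputation enters month 3 as if it were month 6. The all-visit model is exploratory, names only compound symmetry and AR(1), specifies no month-6 contrast, and is not designated as a missing-data check, although a divergence could be noticed there.

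A second reply is that the bias needs selection that differs by arm. Table 2 expects the commonest cause of missing data, health reasons, to be the same in both arms, and with equal selection the two- and three-point models agree. The 40% is a stated maximum; the team reports 0-4% loss at 12 months in its other COPD studies. All of this stands and limits how likely and how large the bias is. It does not favor the two-point model, which had no advantage in estimate and only a larger standard error under random drop-out.

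A third reply is that the precision gain is small. It is.

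**Conclusion.** The point holds as a specification gap with two possible consequences. On observed data, the two-point model is off by roughly 4 to 10 m in either direction if drop-out depends on month-3 response differently by arm (assumed correlations 0.65-0.85, 15% and 25% loss before and after month 3, one-sided selection at half to full strength). It is off by about zero if drop-out is random or equally selective. If the imputation rule governs, the effect is pulled toward zero, to about 34-43 m against 54 m with an assumed 27 m at month 3.

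A reader might infer that the trial will overstate its effect by about 8.5 m or test at 11%. The documents do not support that: those figures require both an observed-data analysis and selection in WEB only. The plan leaves the first open and gives no evidence for the second. The documents also give no correlations, and no share of drop-outs who attend month 3. The sample size is unaffected. This should be changed before analysis, but it does not invalidate the design.

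**What to change.** **Statistics (power analysis), Primary Aim.** Fit the primary PROC MIXED to observed 6MWT at baseline, month 3 and month 6, with time as a class variable and unstructured covariance. Name the month-6 between-arm contrast as the primary estimate.

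**Secondary Aims.** Do the same for the secondary outcomes measured at month 3. Keep month 12 in the additional analyses.

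**Minimizing Attrition and Handling Missing Data, and Table 2.** State that the primary model uses observed data without single imputation, and move the last-observed and least-favorable imputations to sensitivity analyses. This part is essential: if month 6 is already filled in, adding month 3 to the model leaves the month-6 contrast essentially unchanged.

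**Cost.** A few sentences, no new data and no change in sample size. The unstructured matrix goes from 3 to 6 parameters (three more), plus the month-3 fixed effects. There is no benefit for drop-outs who miss month 3, and under random drop-out the standard error falls by only a few percent.

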Based on our previous work, medical problems and temporary suspension from the exercise program will be the most common reason for missing outcomes data in both arms. We have designed the testing windows to minimize missing data. At months 3 and 6, testing will be allowed within a window of  $\pm 2$  weeks. At months 9 and 12, testing will be allowed within a window of  $\pm 1$  month, making the total participation time up to 13 months from the baseline in-clinic study visit (C00). Despite our efforts at follow-up, some missing data are expected with multiple testing visits. We will collect the reasons for missing data such as death, COPD exacerbation, medical reasons, or non-medical reasons. We will compare the rate of losses to follow-up at 3, 6, 9, and 12 months among the two arms using the chi-square test of association. We will assess whether any baseline characteristics such as age, FEV1 % predicted, or 6MWT distance, are associated with losses to follow-up using chi-square tests for categorical baseline data and analysis of variance for continuous baseline data. If baseline variables and treatment group are found to be associated with loss to follow-up, then the analysis models will be modified to include the differing baseline variables as covariates to provide unbiased estimates of intervention effects. For subjects who discontinue the study early due to worsening of COPD or due to death, missing outcome data will be imputed using the least favorable data observed prior to discontinuation. Missing data for subjects who miss a visit not related to worsening of COPD will be imputed using last observed data. We will also perform sensitivity analyses using the complete case method, excluding those with no observed outcome at 6 months.

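### The primary mixed model names no deciding test and does not adjust for baseline 6MWT; one baseline-adjusted month-6 contrast should be fixed as the primary analysis

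*Combined protocol and SAP*

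**What the plan says.** The target is clear. Specific Objectives, Work Proposed and the Statistics section all point to 6MWT distance at month 6. The Primary Aim paragraph opens "We focus on 6MWT distance at 6 months", and the Power Calculation states "Our main comparison is 6MWT distance at 6 months between the WEB intervention and control arms".

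The model is described separately. It is a two-way ANOVA fitted in PROC MIXED, "using absolute measures of 6MWT distance at baseline and 6 months". "Models will have 6MWT distance as the dependent variable, and treatment, time, and treatment-time as independent variables". The plan says this will "allow us to assess the effect of treatment (intervention versus control), and additionally allow us to assess the interaction between treatment and time". On covariates, "models will also include study site and any unbalanced baseline characteristics as covariates".

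Minimizing Attrition and Handling Missing Data lists baseline 6MWT among the variables to be checked against loss to follow-up, and would add it to the model only if an association is found. The same section says: "Missing data for subjects who miss a visit not related to worsening of COPD will be imputed using last observed data". Additional Analyses uses the same three terms over all visits and does not rank them. The Secondary Aims text repeats the primary wording for the continuous secondary outcomes.

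**The concern.** A model with treatment, time and their interaction yields at least three candidate answers: the treatment effect averaged over baseline and month 6, the interaction (difference in change), and the treatment difference at month 6. They have different p-values, and the plan does not say which one answers its declared question. The averaged effect, which the paragraph lists first, includes a baseline visit at which randomisation makes the expected difference zero, so it estimates half of the month-6 effect.

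The second issue is efficiency. With baseline as an outcome and arm means free to differ there, the month-6 contrast gains precision only from participants who have a baseline but no month-6 value. If missing values are filled in as the attrition section says, nobody is in that position, and before other covariates the contrast is the plain difference in month-6 means. Baseline 6MWT is collected on everyone and could do more. Choosing other covariates after seeing imbalance also leaves the primary model open until the data are in hand.

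**Working it through.** **Inputs from the Power Calculation.** Difference 54 m; SD 100 m, with "the published standard deviation for 6MWT distance of 80-120 meters" as the wider range; 55 evaluable per arm; 40% drop-out; 185 randomised, 111 evaluable; alpha 0.05, taken as two-sided because a one-sided test would need only 43 per arm. **Assumption.** The correlation r between baseline and month-6 6MWT is not in the documents; I use 0.2, 0.5 and 0.7. Powers are from the noncentral t distribution.

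**1. The plan's own figure.** The two-sample t calculation at 54/100 gives 54.8, so 55 per arm, with power 80.1%. 111/(1 − 0.4) = 185. Both reproduce, for a month-6 two-sample comparison.

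**2. Baseline adjustment with 55 per arm.** ANCOVA replaces the SD by SD × √(1 − r²).

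| SD (m) | Unadjusted | r = 0.2 | r = 0.5 | r = 0.7 |
|---|---|---|---|---|
| 80 | 94% | 95% | 98% | >99% |
| 100 | 80% | 82% | 90% | 98% |
| 120 | 65% | 67% | 77% | 91% |

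**3. The planned mixed model on observed data.** Per arm there are n = 92.5 baselines and m = 55.5 month-6 values, drop-out is taken as unrelated to outcome, and the covariance is unstructured. Each variance below is for the difference between arms, with σ = 100:
- month-6 contrast: 2σ²[(1 − r²)/m + r²/n]
- interaction: 2σ²[(1 − r²)/m + (1 − r)²/n]
- averaged effect (27 m): (2σ²/4)[(1 − r²)/m + (1 + r)²/n]
- month-6 contrast with a common baseline mean: 2σ²(1 − r²)/m

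For example, at r = 0.5 the month-6 contrast has variance 2 × 10,000 × (0.75/55.5 + 0.25/92.5) = 324, so SE 18.0 m. With a common baseline mean it is 2 × 10,000 × 0.75/55.5 = 270, so SE 16.4 m.

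| Output | SE in m (r = 0.2 / 0.5 / 0.7) | Power |
|---|---|---|
| Month-6 contrast | 18.8 / 18.0 / 17.0 | 81 / 84 / 88% |
| Interaction | 22.0 / 18.0 / 14.3 | 68 / 84 / 96% |
| Month-6, common baseline mean | 18.6 / 16.4 / 13.6 | 82 / 90 / 98% |
| Averaged effect, 27 m | 12.8 / 13.8 / 14.2 | 55 / 49 / 47% |

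The adjusted contrast gains about 1, 6 and 10 points over the planned month-6 contrast, and about 14, 6 and 1 over the interaction. At SD 120 the planned month-6 contrast has 66, 70 and 75%, against 67, 77 and 91% with a common baseline mean.

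**4. If missing values are imputed.** As an extreme case, 40% drop out at random and baseline is carried forward for all of them. The expected month-6 difference falls to 0.6 × 54 = 32.4 m. In simulation (SD 100, 10,000 runs per setting) power is 57–58% unadjusted; 60, 79 and 94% for the interaction; and 72, 85 and 96% with ANCOVA. The order of the methods is unchanged, and all of them lose effect size.

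**5. Leaving the choice open.** Under equal variances the averaged effect and the interaction are uncorrelated. If a success on either at 0.05 were accepted, the type I error would be 1 − 0.95² = 9.75%.

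**The case against.** The strongest reply is that the plan does declare its target, several times, and the month-6 treatment difference can be taken directly from the planned model. On that reading one sentence is missing, the model is not wrong, and its month-6 contrast already reaches the promised 80% at SD 100 for every r tried. Treating baseline as an outcome is a recognised and unbiased approach under randomisation, so baseline adjustment is a gain in precision whose size depends on a correlation nobody has stated. Baseline 6MWT could also enter the model through the imbalance or drop-out provisions.

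Much of this stands. The averaged-effect reading conflicts with the declared target, so its low power should not drive the judgement, and the 9.75% applies only if either test could count. The carry-forward case is also a worst case: a 6MWT is scheduled at month 3, and if half the drop-outs had that value, unadjusted power would be about 82–83% with the full effect already present at month 3, or about 72–73% with half of it (both are assumptions).

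It does not close the gap. No sentence commits to the month-6 contrast, and the wording offers two other outputs. The routes by which baseline 6MWT might enter depend on the data, and would put it on both sides of a model in which it is already an outcome.

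**Conclusion.** The concern holds and should be fixed. The declared comparison and the primary model are not joined by a named test, and baseline 6MWT is used less fully than it could be. The sample size is right and does not change.

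The need to name one test does not depend on any assumption. The size of the precision gain does: it is negligible at r = 0.2 and substantial at r = 0.7, and it matters most if the SD is near the upper end of the plan's range. In every setting computed, the baseline-adjusted month-6 contrast has at least the power of the other candidates. Confidence is high on the unnamed contrast and on that ranking; the exact gain is uncertain because r is not given.

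**What to change.** In the Primary Aim paragraph, name one primary test: the WEB-minus-control difference in 6MWT at month 6, two-sided 0.05, adjusted for baseline 6MWT and site. Fix both covariates in advance, in place of covariates picked for observed imbalance. Take the contrast either from ANCOVA of month-6 6MWT on baseline 6MWT, or from PROC MIXED with the arms sharing a common baseline mean. State that the treatment effect averaged over baseline and month 6 is not a test of efficacy. Use matching wording for the continuous secondary outcomes, each adjusted for its own baseline.

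The cost is a few sentences in the SAP and a few lines of SAS, with no new data, visits or patients. This does not cure the shrinkage caused by single imputation of missing values, which affects whichever contrast is used and needs its own decision.
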